9 STUDY POPULATION

Eligibility will be reviewed and documented by an appropriately qualified member of the investigator's team before subjects are enrolled.

9.1 Inclusion Criteria

Subjects who meet all of the following inclusion criteria will be eligible.

1. Subject's legally appointed and authorized representative (e.g., parent or legal guardian) will sign and date an ICF and the subject will sign and date an assent form (if applicable).
2. Subjects entering the **Treatment Cohort** must meet both of the following criteria:
 - Completed 24 weeks of study drug treatment in Study 109 or completed 24 weeks of study drug treatment and the Week 26 Safety Follow-up in Study 011B (NOTE: the last dose of study drug is the evening dose administered the day before the Week 24 Visit or the dose at the Week 24 Visit [based on the applicable protocol version for which a subject screens (provides consent/assent) under] in Study 109 or the evening dose administered the day before the Week 24 Visit in Study 011B)
 - Subjects who had study drug interruptions, but completed study visits up to Week 24 of Study 109 or Week 26 of Study 011B are eligible (this is Day 1 of Study 110 for subjects at Study 110 active sites). Subjects who are not taking study drug at the end of the Treatment Period (NOTE: subjects from Study 011B have a planned Washout Period from Week 24 to Week 26 and must still

complete the Week 26 Safety Follow-up), including subjects who require study drug interruption to be either continued or initiated at Day 1 in Study 110, must have received Vertex approval for enrollment in the Treatment Cohort.

- Elect to enroll in the Treatment Cohort

NOTE: Subjects who prematurely discontinued study drug treatment are not eligible for enrollment in the Treatment Cohort.

Subjects entering the **Observational Cohort** must meet 1 of the following criteria:

- Completed 24 weeks of study drug treatment in Study 109 or completed 24 weeks of study drug treatment and the Week 26 Safety Follow-up in Study 011B (NOTE: the last dose of study drug is the evening dose administered the day before the Week 24 Visit or the dose at the Week 24 Visit [based on the applicable protocol version for which a subject screens (provides consent/assent) under] in Study 109 or the evening dose administered the day before the Week 24 Visit in Study 011B), but do not elect to enroll in the Treatment Cohort
 - Subjects who received at least 4 weeks of study drug and completed visits up to Week 24 of Study 109 or Week 26 of Study 011B (this is Day 1 of Study 110 for subjects at Study 110 active sites) but are not taking study drug at the end of the Treatment Period (NOTE: subjects from Study 011B have a planned Washout Period from Week 24 to Week 26 and must still complete the Week 26 Safety Follow-up) because of a drug interruption and did not receive Vertex approval for enrollment into the Treatment Cohort (or elect not to enroll in the Treatment Cohort).
 - Subjects who permanently discontinued study drug after receiving at least 4 weeks of study drug and remained in the study from the time of discontinuation of study drug treatment through the Week 24 Visit in Study 109 or the Week 26 Visit of Study 011B.
3. Subjects who are willing to remain on a stable CF medication regimen through the Safety Follow-up Visit (Treatment Cohort only).
 4. As deemed by the investigator, the subject's legally appointed and authorized representative (e.g., parent or legal guardian) must be able to understand protocol requirements, restrictions, and instructions. The subject's legally appointed and authorized representative should be able to ensure that the subject will comply with, and is likely to complete, the study as planned.

9.2 Exclusion Criteria (Treatment Cohort Only)

Subjects who meet any of the following exclusion criteria will **not** be eligible.

1. History of any comorbidity or laboratory abnormality that, in the opinion of the investigator, might confound the results of the study or pose an additional risk in administering study drug to the subject (e.g., cirrhosis with portal hypertension).
2. Pregnant and nursing females. Females of childbearing potential must have a negative urine pregnancy test at the Day 1 Visit before receiving the first dose of study drug (Section 11.7.2).

3. Sexually active subjects of reproductive potential who are not willing to follow the contraception requirements outlined in Section 11.7.8.
4. History of drug intolerance in the prior study that would pose an additional risk to the subject in the opinion of investigator, and which should be discussed with the Vertex medical monitor. Examples of subjects who may not be eligible for the treatment cohort include (but are not limited to) the following:
 - Subjects with a history of allergy or hypersensitivity to the study drug
 - Liver function test (LFT) abnormality during study drug treatment in the previous study (Study 109 or Study 011B) for which a clear cause was not identified:
 - Abnormal liver function defined as any 2 or more of the following:
 - a. $\geq 3 \times$ upper limit of normal (ULN) aspartate aminotransferase (AST)
 - b. $\geq 3 \times$ ULN alanine aminotransferase (ALT)
 - c. $\geq 3 \times$ ULN gamma-glutamyl transpeptidase
 - d. $\geq 3 \times$ ULN alkaline phosphatase
 - ALT or AST $> 5 \times$ ULN
 - Total bilirubin $> 2 \times$ ULN
 - Other LFT abnormalities that would pose an additional risk to the subject in the opinion of investigator or Vertex
 - Other severe or life-threatening reactions to the study drug in the previous study
5. History of poor compliance with study drug and/or procedures in the previous study as deemed by the investigator.
6. Participation in an investigational drug trial (including studies investigating lumacaftor and/or ivacaftor). NOTE: participation in a noninterventional study (including observational studies, registry studies, and studies requiring blood collections without administration of study drug) is permitted.

9.3 Study Restrictions

For subjects enrolled in the Treatment Cohort, prohibited medications and certain foods are not allowed as summarized in Table 9-1.

A nonexhaustive list of study prohibitions and cautions for food and medication will be provided in the Study Reference Manual.

Table 9-1 Study Restrictions

Restricted Medication/Food^a	Treatment Period
Strong CYP3A inducers	None allowed
Strong CYP3A inhibitors	Use with caution

CYP: cytochrome P450.

Note: The use of restricted medication in subjects with a medical need will be addressed on a case-by-case basis with the medical monitor or authorized designee.

^a See Section 9.4 for guidance for concomitant medications.

9.4 Prior and Concomitant Medications and Other Study Restrictions

9.4.1 Prohibited Medications

Prohibited medications as described in Table 9-1 are not allowed in this study while subjects are receiving study drug.

The use of cytochrome P450 (CYP) 3A substrates is not prohibited in this study, but investigators need to be aware that lumacaftor appears to be a strong inducer of this CYP isoenzyme. Therefore, the efficacy of drugs extensively metabolized by this isoenzyme may be affected. Each investigator should evaluate the benefit/risk ratio of using such drugs with lumacaftor during this study. Investigators should discuss any concerns regarding the use of CYP3A substrates during this study with the Vertex medical monitor or authorized designee.

The use of CYP2C and 2B6 substrates are not prohibited in this study, but investigators need to be aware that lumacaftor has been shown in vitro to induce CYP2B6, CYP2C8, CYP2C9, and CYP2C19; inhibition of CYP2C8 and CYP2C9 has also been observed in vitro. Additionally, in vitro studies suggest that ivacaftor may inhibit CYP2C9. Therefore, concomitant use of lumacaftor in combination with ivacaftor with CYP2B6, CYP2C8, CYP2C9, and CYP2C19 substrates may alter the exposure of these substrates.

Each investigator should evaluate the benefit-risk ratio of using such drugs with lumacaftor and ivacaftor during this study and discuss the use of these substrates during this study with the medical monitor or authorized designee.

The use of strong inhibitors of CYP3A is not prohibited in this study, but investigators need to be aware that a strong inhibitor of CYP3A has been shown to increase the exposure of ivacaftor when given in combination with lumacaftor; however, due to the induction effect of lumacaftor, the net exposure of ivacaftor is not expected to exceed previous experiences with ivacaftor monotherapy. Subjects who are using strong CYP3A inhibitors do not require study drug interruption. However, if they interrupt study drug for more than 72 hours, study drug resumption requires medical monitor discussion and approval. Each investigator should evaluate the benefit-risk ratio of using such drugs with lumacaftor and ivacaftor during this study and discuss the use of these strong inhibitors of CYP3A during this study with the medical monitor or authorized designee.

A nonexhaustive study prohibitions and cautions list for food and medications will be provided in the Study Reference Manual.

9.4.2 Prior and Concomitant Medications

Information regarding all prior and concomitant medications, including the subject's CF medications, other medications, and herbal and naturopathic remedies administered at, or after, completion of treatment in Study 109 or the Safety Follow-up Visit in Study 011B through the Safety Follow-up Visit of this study will be recorded in each subject's source documents and electronic case report form (eCRF).

- It is recommended that subjects continue to remain on a stable medication regimen for their CF from the previous study through the Safety Follow-up Visit in the current study. Stable medication regimen is defined as the current medication regimen for CF that subjects have been following for at least 4 weeks before Day 1.
- Information about bronchodilator use during the study will be collected and documented in the subject's source documents and eCRF. Subjects who are using a bronchodilator should have their spirometry assessments performed according to the guidelines provided in Section 11.6.3.

For subjects enrolled in the Observational Cohort, information regarding all prior and concomitant medications will not be collected.

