6.2 Secondary Objectives

- To evaluate the long-term efficacy and durability of lumacaftor in combination with ivacaftor for subjects in the Treatment Cohort
- To evaluate the post-treatment safety of lumacaftor in combination with ivacaftor for subjects in the Observational Cohort

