The following subjects from Study 109 or Study 011B who meet the study criteria (Section 9.1) and elect to enroll in Study 110 are eligible for enrollment in the Observational Cohort:

- Subjects who received at least 4 weeks of study drug in Study 109 or Study 011B and completed visits up to Week 24 of Study 109 or Week 26 of Study 011B but who are not eligible (Sections 9.1 and 9.2) for the Treatment Cohort with lumacaftor in combination with ivacaftor
- Subjects who received at least 4 weeks of study drug in Study 109 or Study 011B (and did not prematurely discontinue study drug treatment) and completed visits up to Week 24 of Study 109 or Week 26 of Study 011B but who elect not to continue treatment with lumacaftor in combination with ivacaftor

Subjects in the Observational Cohort will not receive study drug and will have regularly scheduled telephone calls for approximately 2 years after their last dose of study drug in Study 109 or Study 011B to assess the post-treatment safety of lumacaftor and ivacaftor combination therapy.

Figure 8-1 Schematic of Study Design

IVA: ivacaftor; LUM: lumacaftor; q12h: every 12 hours.

- ^a The following subjects may be eligible for enrollment in the Treatment Cohort: (1) subjects who completed 24 weeks of study drug treatment (i.e., lumacaftor in combination with ivacaftor or placebo) in Study 109 or completed 24 weeks of study drug treatment and the Week 26 Safety Follow-up in Study 011B (NOTE: the last dose of study drug is the evening dose administered the day before the Week 24 Visit or the dose at the Week 24 Visit [based on the applicable protocol version for which a subject screens (provides consent/assent) under] in Study 109 or the evening dose administered the day before the Week 24 Visit in Study 011B) and (2) subjects who are not receiving study drug treatment at the end of the Treatment Period in Study 109 or Study 011B (NOTE: subjects from Study 011B have a planned Washout Period from Week 24 to Week 26 and must still complete the Week 26 Safety Follow-up), including subjects that require study drug interruption to be either continued or initiated at Day 1 in Study 110, AND who have received Vertex approval for entry. Subjects who prematurely discontinued study drug treatment are not eligible for enrollment in the Treatment Cohort.

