8.1.1.3 Early Treatment Termination

Subjects who prematurely discontinue study drug treatment during the Treatment Period in Study 110 will be asked to complete the Early Treatment Termination Visit and the Safety Follow-up Visit. The Early Treatment Termination Visit assessments are listed in [Table 3-1](#).

The Early Treatment Termination Visit should be scheduled as soon as possible after the subject decides to terminate study treatment. If the Early Treatment Termination Visit occurs 3 weeks or later following the last dose of study drug, then the Safety Follow-up Visit will replace the Early Treatment Termination Visit (i.e., the assessments performed will be those specified for the Safety Follow-up Visit in [Table 3-1](#)), and an Early Treatment Termination Visit will not be required.

With the exception of [REDACTED] subjects who cannot access the commercial product after regulatory approval because reimbursement by the subject's insurance carrier (whether government or private payer) is not yet available or because the subject lacks insurance coverage, subjects who become eligible to receive commercially-available LUM/IVA by prescription of a physician may be discontinued from study drug dosing and will complete the Early Treatment Termination Visit (before commercially-available LUM/IVA dosing begins). The Safety Follow-up Visit will not be required if the subject immediately continues on commercially-available LUM/IVA.

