8.1.2.2 Long-term Follow-up

Subjects in the Observational Cohort will be followed for approximately 2 years. A telephone contact will be made every 3 to 4 months during the first year and at approximately 2 years (\pm 4 weeks) as shown in [Table 3-2](#).

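### LUM/IVA use after entry to the Observational Cohort is neither barred nor systematically recorded, so its SAEs cannot be reliably sorted into off-drug and on-drug events

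*Protocol*

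**What the plan says.** The cohort's one objective is in Protocol Section 6.2: "To evaluate the post-treatment safety of lumacaftor in combination with ivacaftor for subjects in the Observational Cohort". Its one endpoint is SAEs (Section 7.2). Section 8.1 sets the follow-up: "Subjects in the Observational Cohort will not receive study drug and will have regularly scheduled telephone calls for approximately 2 years after their last dose" in the parent study.

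On medication records, Section 9.4.2 is explicit: "For subjects enrolled in the Observational Cohort, information regarding all prior and concomitant medications will not be collected". Table 3-2 schedules consent, inclusion review, telephone contacts and SAEs, and nothing else. SAEs are collected from consent to the last telephone contact.

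On what is barred, the heading of Section 9.2 confines all exclusion criteria to the Treatment Cohort. Criterion 6, which names LUM/IVA trials, is among them. Section 9.3 is limited in the same way: "For subjects enrolled in the Treatment Cohort, prohibited medications and certain foods are not allowed as summarized in Table 9-1".

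Commercial supply is foreseen in Section 8.1.1.3: "subjects who become eligible to receive commercially-available LUM/IVA by prescription of a physician may be discontinued from study drug dosing". That rule concerns subjects on study drug.

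For the analysis, Protocol Section 12.4.4.1 plans a summary table of all Observational Cohort SAEs, and SAP Section 10.4.1 plans a listing of them. SAP Section 10.1 limits this cohort's summaries to disposition, demographic and baseline characteristics, and SAEs.

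**The concern.** A post-treatment safety question depends on knowing that the child was off the drug when the event occurred. Here the plan opens a route back to the drug and does not ask whether it was taken.

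The error can run in either direction. An SAE in a child who has resumed LUM/IVA could be read as a late effect of drug stopped long before. A quiet SAE record could partly reflect children who are back on treatment. The primary endpoint and every Treatment Cohort analysis are untouched. What is at stake is the cohort's only stated purpose.

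**Working it through.** The plan gives no figure to reproduce. Table 12-1 shows the precision of a CF lung incidence at n = 256 and does not give the size of the Observational Cohort. The check is therefore a comparison of provisions.

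1. **Is LUM/IVA use barred after entry?** No bar was found. Section 8.1 withholds Study 110 study drug from this cohort, but that does not reach prescriptions or other trials. The exclusions (9.2), the food and drug restrictions (9.3, where Table 9-1 names only strong CYP3A inducers and inhibitors) and the stable-regimen criterion (9.1, item 3) are all limited to the Treatment Cohort.

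2. **Is such use plausible?** For some children, yes. Section 9.1 admits those who completed 24 weeks and chose not to join the Treatment Cohort, and those with an interruption who lacked sponsor approval. For dosed subjects the sponsor thought about commercial supply closely enough to place the Early Treatment Termination Visit before commercial dosing begins (8.1.1.3). There is no counterpart for this cohort.

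3. **Is it recorded?** Not systematically. The footnote to Table 3-1 on telephone contacts has sites ask about concomitant medications. Table 3-2 has no such footnote, and 9.4.2 rules out collecting them. Two other items come close. Section 13.1.1.3 lists medication or other treatment given among the data for each AE, but 13.1.1.8 describes this as treatment for the event. Section 13.1.2.2 has the investigator consider possible causes of each SAE. Neither requires a LUM/IVA start or stop date.

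4. **Can the output separate the events?** No rule does so. Neither 12.4.4.1 nor SAP 10.4.1 provides a flag, cut-off or split by exposure. The narrative listings in SAP 10.5 cover Treatment Cohort Periods 1 and 2 only.

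5. **Does 'post-treatment' apply to every child?** Not necessarily. Study 109 compared active drug with placebo (8.2.1), and 9.1 accepts at least 4 weeks of study drug without saying which. Some children may never have taken LUM/IVA, so later commercial use would be their first exposure.

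Taken together, three different children can appear alike in the planned output: one who stopped active drug and stayed off it, one who was back on LUM/IVA when the event occurred, and one who had only placebo in Study 109.

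**What the existing calls could capture.** Calls every 3 to 4 months give 12/4 = 3 to 12/3 = 4 contacts in year 1, plus one at about 2 years, so 4 to 5 in all. From the end of year 1 to the last call is about 24 − 12 = 12 months, so dates in year 2 would rest on recall of up to about a year.

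**The case against.** The best defence is that SAE-only telephone follow-up is a deliberate light-touch choice for a secondary, descriptive objective, and that the safety system is not blind. The investigator assesses each SAE for causes and follows it to resolution (13.1.2.2), the sponsor may inspect medical records (13.2.4 and 13.2.5), and discrepant data are queried (13.3). A restart in a child with an SAE could surface this way. The eCRF and SAE form are not among the documents, and the text on exceptions to the commercial-supply rule is redacted, so some capture may exist out of sight.

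Much of this stands, and it rules out three stronger readings that a reader might infer:

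- *That the plan will report on-drug SAEs as post-treatment SAEs.* Neither document applies that label to this cohort's events. The SAP's defined post-treatment AE category belongs to the Treatment Cohort periods. The label comes only from the objective.
- *That re-exposed children can never be identified.* Records and queries could identify some, particularly those with an SAE.
- *That some stated share of follow-up time is contaminated.* Such a share needs a restart proportion and a restart time, and the documents give neither. No person-time rate is planned for this cohort; events per 100 patient-years belong to Treatment Cohort Period 1 (SAP 10.1.2.1). Many entrants may also be unlikely to restart, having discontinued permanently or been ineligible for further treatment.

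What does not stand is that incidental discovery is enough. It depends on someone thinking to ask, it need not produce dates, and it leaves no trace in children without an SAE.

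**Conclusion.** The concern holds in a limited form. The plan neither prevents nor systematically captures LUM/IVA use after entry to the Observational Cohort, and it pools all SAEs, so the output cannot reliably answer the off-drug question that the cohort was set up to answer. This follows from stated rules (9.4.2, 9.2, 9.3, Table 3-2, 12.4.4.1 and SAP 10.4.1), not from missing detail alone.

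The number of SAEs affected is unknown and could be zero. The conclusion assumes only that some children in the cohort could obtain LUM/IVA during follow-up, which the protocol's own provision for commercial supply makes reasonable. It also assumes that the unseen forms hold no dedicated restart field, in line with 9.4.2. Because the objective is secondary and descriptive, this is a change worth making rather than a threat to the trial's main conclusions.

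**What to change.** - **Protocol 9.4.2 and Table 3-2:** at Day 1 and at each existing telephone contact, record any LUM/IVA or other CFTR modulator use, commercial or in a trial, since the last contact. Take start and stop dates, marked approximate where recalled. Confirm this use again whenever an SAE is reported.
- **SAP 10.4.1:** keep listing every Observational Cohort SAE. Add one flag for parent-study treatment (active or placebo) and one for whether the event came before or after first LUM/IVA or other modulator use since the parent study. Carry the same flags into the table in Protocol 12.4.4.1 if it is kept.
- **Interpretation:** read as post-treatment only those SAEs that occur in children who received active drug in the parent study and before any such use. Show the rest separately.
- **Follow-up:** all children stay in follow-up. The change concerns recording and reporting only and does not touch treatment.

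The cost is one eCRF item asked in calls already scheduled and two flags in one output. There are two drawbacks. Year-2 dates will be imprecise because of the long recall interval, though asking at the time of each SAE limits this where it matters most. Fewer events will also count as purely post-treatment.

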9.5 Removal of Subjects From Study Drug Treatment

Subjects may discontinue study drug treatment at any time if the subject, investigator, or Vertex determines that it is not in the best interest of the subject to continue treatment.

The investigator should inquire about the reason for withdrawal, request that the subject return all unused study drug, and request that the subject return for an Early Treatment Termination Visit and Safety Follow-up Visit. If a subject does not return for a scheduled visit, every effort should be made to contact the subject. In any circumstance, every effort should be made to document subject outcome, if possible.

A subject will be withdrawn from study drug treatment for the following reason:

- A female subject or a female partner of a male subject has a confirmed pregnancy

A subject may be withdrawn from study drug treatment after a discussion between the investigator and the medical monitor, for any of the following reasons:

- A subject develops a medical condition that requires prolonged concomitant therapy with a prohibited medication or prolonged interruption of the study drug.
- A subject develops a life-threatening AE or an SAE that places him/her at immediate risk, and discontinuation of study drug treatment and withdrawal from the study is deemed necessary.
- A subject is noncompliant with the study requirements.
- A subject has an increase in transaminases according to evaluations and management described in Section 11.7.3.
- A subject has an increase in QTc according to evaluations and management described in Section 11.7.5.

- With the exception of [REDACTED] subjects who cannot access the commercial product after regulatory approval because reimbursement by the subject's insurance carrier (whether government or private payer) is not yet available or because the subject lacks insurance coverage, subjects who become eligible to receive commercially-available LUM/IVA by prescription of a physician may be discontinued from study drug dosing and will complete the Early Treatment Termination Visit (before commercially-available LUM/IVA dosing begins). The Safety Follow-up Visit will not be required if the subject immediately continues on commercially-available LUM/IVA.

